	
assumed for part 2, that also the number of patients with combination therapies in part 2 (n = 300) will grant a representative statement to all research questions. Based on information of urological and oncological experts as well as own data of the GermanOncology ^{*1} network (see below), the following assumptions could be set:
 
• Number of patients with new 1L in urological practices (per practice 1- 3 urologists) = 4 - 6 per year
○ Number of patients with new 1L in period of 24 months = 8 - 12• Number of patients with new 1L in oncological practices (per practice 2- 4 oncologists) = 4 - 6 per year
○ Number of patients with new 1L in period of 24 months = 8 - 12• Number of patients with new 1L in hospitals with urological focus = 8 - 12 per year
○ Number of patients with new 1L in period of 24 months = 16 - 24• Proportion of 1L therapies in urological and oncological practices: 50% : 50%• Proportion of patients treated with 1L in practices and hospitals (as most of therapies are oral therapies): 65% : 35% 
Based on the assumptions the needed number of sites are at least:
 
• Number of urological practices: 15• Number of oncological practices: 15• Number of hospitals with urological focus: 10• Total number of sites across Germany: 40 
<small>^{*1} GermanOncology operates a permanent network of 25 oncological practices across Germany, is collecting longitudinal RWE data about several tumor entities since 2012 and is able to analyze data from more than 25.000 patients with around 25 different tumor entities</small>

Data Analysis	
The following clinical outcomes will be measured:
 
Primary outcome:
 
○ PFS in 1L:
▪ described as median and rates of patients without disease progression or death for any cause at defined timepoints (6, 9, 12 and 18 months) after start of 1L therapy. 
Secondary outcomes:
 
○ OS in 1L

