	
 ▪ Defined as median and rates of patients alive at pre-defined timepoints (12 and 18 months) after start of 1L therapy. ○ Proportion of different drug regimen in 1L 
 ▪ Defined as percentages of therapy protocols used as 1L therapy. ○ Best response rate (RR) in 1L 
 ▪ Defined as best response (complete response (CR) / partial response (PR) / stable disease (SD) / progressive disease (PD) / not done (ND)) recorded from the start of the therapy until disease progression/recurrence based on investigator's assessment. A confirmation of response is not required. ○ Duration of Response (DoR) in 1L 
 ▪ Defined as time from documentation of first disease response to disease progression. ○ Time to progression (TTP) in 1L 
 ▪ Defined as time from start of therapy until objective disease progression without including deaths. ○ Time to next treatment (TTNT) in 1L 
 ▪ Defined as time from last drug administered to initiation of next therapy. ○ Dose modifications and discontinuations in 1L 
 ▪ Defined of number of patients with at least 1 dose modification (reduction of dose or cancelling of administration) or with an interim/permanent discontinuation of one or all drugs of a therapy. ○ Handling after dose modification or discontinuations in 1L 
 ▪ Defined as continuation of therapies after dose modifications or temporary/permanent discontinuation of single drugs. 
The clinical outcomes will be analyzed for the total group of all patients and for following subgroups:
 
 ○ Age: < 70 years vs. ≥70 years ○ Gender: male vs. female ○ Risk rating: favorable (low) vs. intermediate vs poor (high) risk ○ Medical disciplines: urology vs. medical oncology ○ Institutions: practices vs. hospitals
Milestones	
Planned milestones:
 
 ● Start of data collection: 1 October 2022 ● Interim analysis (expected): 31 October 2022 ● End of data collection: 30 January 2023 ● Final study report: 15 April 2023

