8.1. Primary Research Questions

Based on the above background, there are currently a number of unanswered questions for health services research:

- How is the effectiveness, defined as measurement of beneficial effects under “real world” clinical settings, (e.g. progression-free survival, overall survival and best response) of TKI and/or ICI as 1L in patients with aRCC?
- How are patients with aRCC treated in 1L under daily care conditions in Germany in general and in accordance to medical specialities (urology and medical oncology) and treatment settings (hospitals vs office-based practices)?
- Are all patients assigned to individual risk ratings under standard daily care conditions according to a scale developed by the IMDC before start of a 1L?
- How are patients treated in 1L in different risk rating groups and how is the adherence to national/international guidelines?
- What kind of previous and subsequent therapies are administered before and after 1L?
- How often are evaluations for PD-L1 expression performed before start of 1L and how many patients are positive (TPS $\geq 1\%$) or negative?

- How long are patients treated with TKI + ICI and ICI + ICI in 1L in general and in relation to specific therapies like avelumab + axitinib?
- How frequent are dose modifications and early discontinuations and what are the reasons?
- Are there differences in the handling of modifications among medical disciplines?

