8.2. Study Objectives

To answer these questions the following objectives are derived:

Primary Objective(s):

- Progression-free survival (PFS) for 1L therapies, expressed as median and as rates at timepoints of 6, 9, 12 and 18 months after start of 1L

Secondary Objectives:

- Overall survival (OS) of 1L therapies, expressed as median and rates at timepoints of 12 and 18 months after start of 1L therapy
- Best response in 1L overall and in dependence of administered drug regimen
- Progression-free survival of 1L therapies in dependence of specific drug regimen
- Pre- and post-treatments (i.e. surgery, radiotherapy, medicinal therapies) before/after TKI + ICI and ICI + ICI in 1L
- Duration of response (DoR) in 1L overall and in dependence of administered drug regimen (TKI + ICI or ICI + ICI)
- Frequency of dose modifications and temporary/permanent discontinuations of 1L therapies and their reasons
- Proportions of modifications by dose reduction compared to cancelling single applications
- Effectiveness (PFS, OS and best response) of administered 1L therapies under real world conditions by medical specialty (urology, medical oncology) and setting (practice, hospital)

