9.1.2. Exclusion criteria

Exclusion criteria for part 1 and 2

Patients meeting the following criteria will not be included in the study:

- Patients participating in an interventional clinical study within 30 days before start of 1L

All sites are asked to document all of their patients with the fulfilled inclusion and not fulfilled exclusion criteria, starting with the earliest start (in part 1) and the longest follow-up period (in part 2), respectively. The patients should be treated with the systemic 1L therapy in the site and data should be available in the medical records of the sites. The enrollment will be competitively over all participating sites without a limitation for the single sites. In part 2 quotas for groups with ICI + TKI and ICI + ICI and with the specific therapy avelumab + axitinib or nivolumab + ipilimumab will be set up.

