9.4. Study size

Based on public data the population of patients with aRCC and an indication for a 1L therapy is around $n = 4.500 - 5.000$ patients per year ([Robert Koch Institute 2020](#)). In the period of 01 January 2020 – 31 December 2021, which is the main period of interest in the study for completing or starting 1L therapies, the total population of patients with aRCC would be around $n = 9.000 - 10.000$ patients. To estimate the needed number of patients in the study to reach adequate representation across Germany, the following common formula is used

$$n = \frac{z^2 \pi(1 - \pi)N}{z^2 \pi(1 - \pi) + E^2(N - 1)}$$

N = population of patients with aRCC and indication for 1L = 10.000 patients in 24 months

$\Pi = 0,5$ (consensus, if attribute is unknown before study)

E = margin of error = 5% = 0,05

$Z = 1,96$ (for confidence interval of 95%)

Based on these assumptions (PFS of 1L therapies included in guidelines was 8.4 – 151 months in clinical studies) the number of patients needed for representative statement regarding the primary objective (= PFS rates at defined time points under real world conditions) is at least $n = 370$. With a buffer of around 10% the sample size in the study should be $n = 400$ patients with aRCC and 1L therapies in the period from 01 January 2020 – 31 December 2021. Based on published data for PFS it could be assumed for part 2, that also the number of patients with combination therapies in part 2 ($n = 300$) will grant a representative statement to all research questions. Based on information of urological and oncological experts as well as own data of the GermanOncology *¹ network (see below), the following assumptions could be set:

- Number of patients with new 1L in urological practices (per practice 1- 3 urologists) = 4 - 6 per year
 - Number of patients with new 1L in period of 24 months = 8 - 12
- Number of patients with new 1L in oncological practices (per practice 2- 4 oncologists) = 4 - 6 per year
 - Number of patients with new 1L in period of 24 months = 8 - 12
- Number of patients with new 1L in hospitals with urological focus = 8 - 12 per year
 - Number of patients with new 1L in period of 24 months = 16 – 24
- Proportion of 1L therapies in urological and oncological practices: 50% : 50%
- Proportion of patients treated with 1L in practices and hospitals (as most of therapies are oral therapies): 65% : 35%

Based on the assumptions the needed number of sites are at least:

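### Part 2 is enrolled by regimen quotas of unstated size and basis, yet its pooled results are called representative and no weighting is described

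*Combined protocol and SAP*

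**What the plan says.** Section 9.1.2 closes with the enrolment rule. Sites are told: "All sites are asked to document all of their patients with the fulfilled inclusion and not fulfilled exclusion criteria". The rule for the second part then follows: "In part 2 quotas for groups with ICI + TKI and ICI + ICI and with the specific therapy avelumab + axitinib", with nivolumab + ipilimumab named as a further group. No number is attached to any quota. The text does not say whether a quota is a minimum, a cap or a fixed count, or whether it was derived from the treatment mix in Germany.

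The Abstract (Study Size) and section 9.4 both make the claim for the second part. In the Abstract it reads "the number of patients with combination therapies in part 2 (n = 300) will grant a representative statement to all research questions". The only sample-size formula in section 9.4 is a finite-population formula for one proportion, applied to all first-line patients. The 300 has no derivation of its own.

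Several planned results are pooled. The Abstract (Data Analysis) states: "The clinical outcomes will be analyzed for the total group of all patients and for following subgroups". The subgroups listed are age, gender, risk rating, discipline and institution; regimen is not among them. Section 8.1 asks "How long are patients treated with TKI + ICI and ICI + ICI in 1L in general and in relation to specific therapies". Section 8.2 asks for duration of response both overall and by combination type, and for PFS and best response by regimen.

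Section 9.6 leaves detailed methods to a separate SAP. Section 9.8 (limitations) does not mention the quotas.

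**The concern.** A pooled estimate is an average of regimen-specific results, weighted by each regimen's share of the sample. If quotas set those shares, and they differ from the shares in routine care, the pooled figure answers a question about the sample and not about German practice. A larger sample does not remove that difference.

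Section 7 assigns the effectiveness of combinations and the handling of their intolerabilities to Part 2. The figures at stake are therefore overall modification and discontinuation frequency, treatment duration, duration of response and PFS for combination therapy. The same applies one level down: avelumab + axitinib has its own quota inside ICI + TKI, so an ICI + TKI figure pooled over partner drugs can move as well.

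The two enrolment rules also pull against each other. A quota that closes would stop a site from documenting all its eligible patients.

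**Working it through.** **The plan's own figure.** Section 9.4 uses n = z²π(1−π)N / [z²π(1−π) + E²(N−1)] with z = 1.96, π = 0.5, E = 0.05, N = 10,000:

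9,604 / (0.9604 + 24.9975) = 369.98, so 370. It reproduces. The formula treats the patients as a simple random sample and makes no allowance for quotas.

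**Precision at n = 300.** Half-width = 1.96 × √(0.25/300) = 5.7 points (5.6 with the finite-population correction at N = 10,000). This is the yardstick for the shifts below.

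**Shift within ICI + TKI.** Section 8 gives axitinib dose reduction of 42% with avelumab + axitinib and 20.3% with pembrolizumab + axitinib. If avelumab + axitinib has share w among these two, pooled = 42w + 20.3(1 − w):

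- w = 0.20: 8.40 + 16.24 = 24.6%
- w = 0.50: 21.00 + 10.15 = 31.2%
- w = 0.80: 33.60 + 4.06 = 37.7%

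The range is 13 points, from mix alone. The shares are assumed; the two rates are the protocol's.

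**Shift between ICI + TKI and ICI + ICI.** Section 8 gives interruption of either drug in 69.9% with pembrolizumab + axitinib, and dose delay in up to 58% with nivolumab + ipilimumab. The definitions differ between the studies, so this is only indicative. Pooled = 69.9w + 58(1 − w), with w the ICI + TKI share:

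- 50:50 gives 63.95%
- 60:40 gives 65.14%, a difference of 1.2 points from 50:50
- 75:25 gives 66.93%, a difference of 3.0 points
- 85:15 gives 68.12%, a difference of 4.2 points

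For discontinuation (30.5% against up to 22%), the same mixes differ from 50:50 by 0.9, 2.1 and 3.0 points. All of these lie below 5.7 points.

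**PFS at 12 months.** Assume exponential PFS, S(12) = 0.5^(12/median). Section 8 gives medians of 15.1 to 23.9 months for ICI + TKI. No median is given for ICI + ICI, so the Abstract's range for guideline therapies, 8.4 to 15.1 months, is assumed for it. Moving the ICI + TKI share from 80% to 50% changes pooled 12-month PFS as follows:

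- medians 15.1 and 8.4: 53.5% to 47.4%
- medians 23.9 and 8.4: 63.9% to 53.9%
- medians 23.9 and 15.1: 68.0% to 64.1%
- medians 15.1 and 15.1: no change

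**Cost of re-weighting.** If a 50:50 sample is weighted to a true ICI + TKI share t, the Kish design effect is t²/0.5 + (1 − t)²/0.5:

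- t = 0.60: 1.04, effective n = 300/1.04 = 288, half-width ±5.8 points
- t = 0.70: 1.16, effective n = 259, half-width ±6.1 points
- t = 0.80: 1.36, effective n = 221, half-width ±6.6 points

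**The case against.** The strongest reply is that the protocol does not say what the quotas are. Quotas proportional to real use, or minimums that ordinary accrual meets anyway, would distort nothing. This stands. A reader might infer that the quotas fix the regimen mix at values the sponsor chose and that the overall figures are therefore wrong. The documents support only the conditional statement: the quotas may do this, and nothing shows that they will not.

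A reader might also set the 42% dose reduction against none at all for ICI + ICI and infer a large error in overall modification frequency. The documents do not support that either. The 42% belongs to one regimen. The outcome defined in the Abstract also counts cancelled administrations and discontinuations, and section 8 calls the situation for nivolumab + ipilimumab comparable. On the interruption and delay figures the shift is small.

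Three further points carry weight:

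- By-regimen PFS, best response and duration of response are already planned, and quotas on regimen do not distort single-regimen results. By-regimen modification frequency, however, is not explicit in section 8.2.
- The aim of a regimen distribution representative for Germany belongs to Part 1 (section 7), for which no quotas are stated, and the 370/400 calculation concerns all first-line patients. The total-group sentence in the Abstract does not single out Part 2. The representativeness claim for the 300 patients does.
- The SAP is separate, so weighting may be defined there. But the quotas act at enrolment and the claim stands in the protocol, so a SAP alone would not settle the matter.

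**Conclusion.** The point holds in conditional form. The protocol calls the 300 Part 2 patients representative for every research question while enrolling them by regimen quotas with no stated size, type or basis, and it describes no weighting. Unless the quotas are proportional or do not bind, unweighted pooled Part 2 figures, and ICI + TKI figures pooled over partner drugs, do not support that claim.

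No single size can be given, because neither the quotas nor the true regimen shares are stated. On the protocol's background rates and assumed shares, the effect runs from about 1 to 4 points (interruption or delay) to 13 points (axitinib dose reduction across the two axitinib combinations). The PFS shift runs from none to 10 points, under an exponential model and assumed ICI + ICI medians. The larger values exceed the ±5.7-point half-width at n = 300. This should be corrected, but it does not undermine the single-regimen results.

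**What to change.** In the protocol, with matching text in the SAP:

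1. State each Part 2 quota's size, its type (minimum, cap or fixed) and its basis, and reconcile it with the instruction to document all eligible patients.
2. Make by-regimen results the main Part 2 output, and name modification and discontinuation frequency explicitly among them.
3. For any pooled Part 2 figure, weight each regimen by its share among combination therapies in Part 1, or omit the pooled figure. Label the weights approximate: Part 1 samples by start of first-line therapy and Part 2 by its completion with at least 3 months' follow-up. Weighting corrects the regimen mix only, not the restriction to patients who completed first-line therapy.
4. Remove the word representative for unweighted Part 2 totals, and list the quotas as a limitation in section 9.8.

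The cost is wording plus one weighting step. Regimen is already captured (Table 2), so no new data are needed. Intervals for weighted totals widen somewhat, for example to between ±5.8 and ±6.6 points against ±5.7 if a 50:50 sample is weighted to shares of 60:40 to 80:20.

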9.2. Variables

The following variables will be captured by a specific eCRF and are needed for the analysis of all outcomes and for answering all research questions.

Tab. 2: List of all variables, role, data source and operational definitions

Variable	Role	Data source(s)	Operational definition
Age and gender	baseline characteristic	Medical Chart	Years; male/female
Weight and body surface	baseline characteristic	Medical Chart	kg, m ²
Date of first diagnosis	baseline tumor characteristic	Medical Chart	dd/mm/yyyy
Stage and risk rating (IMDC) at first diagnosis and at start of 1L	baseline tumor characteristic	Medical Chart	Favorable risk / intermediate risk / poor risk
Assessments and results of PD-L1 expression as TPS	baseline tumor characteristic	Medical Chart	y/n; 0-100%
Non-medicinal pre-treatments (primary OP, cytoreductive nephrectomy radiotherapy)	baseline tumor characteristic	Medical Chart	y/n; dd/mm/yyyy of OP; mode of OP; intention of OP (curative/palliative); period and dose of radiotherapy
Medicinal pre-treatments (adjuvant, neoadjuvant)	baseline tumor characteristic	Medical Chart	y/n; start/stop and used therapy protocol
Location of administration and performing medical discipline	Relevant for outcomes	Medical Chart	Urological practice; hematological practice; hospital with urological department; hospital with oncological department
Administered drugs / protocols in 1L	Relevant for outcomes	Medical Chart	administered therapy protocol
If applicable: Reason for ineligibility of ICI	Relevant for outcomes	Medical Chart	Concomitant disease; patient's wish
Duration of 1L	Relevant for outcomes	Medical Chart	Start/stop of therapy or every cycle;

Dates of administrations for i.v. drugs in 1L	Relevant for outcomes	Medical Chart	Dates of every administration
Dosages per administration	Relevant for outcomes	Medical Chart	Dose of administered drugs per administration
Dose modifications or drug administration cancelling or interim/permanent discontinuations of single drugs / complete therapy in 1L	Relevant for outcomes	Medical Chart	Each for single/all drugs: Dose modification; cancelling single administration; temporare discontinuation; permanent discontinuation
Reasons for modifications, cancelling of single administrations and discontinuations in 1L	Relevant for outcomes	Medical Chart	Each for single/all drugs: intolerance; age; performance status; patient's decision; other
Supportive drugs prescribed during 1L	Relevant for outcomes	Medical Chart	Administered supportive drugs in connection with cancer therapy
Date of first response and best response in 1L incl. date and mode of assessment	Relevant for outcomes	Medical Chart	dd/mm/yyyy; CT/MRI/ultrasound/x-ray; clinical assessment; laboratory
Assessment of first and best response in 1L	Relevant for outcomes	Medical Chart	CR/PR/SD/PD/ND
Date of tumor progression	Relevant for outcomes	Medical Chart	dd/mm/yyyy
Reasons for end of 1L	Relevant for outcomes	Medical Chart	Progression; intolerance; decision oncologist; patient's wish; death; deterioration performance
Subsequent therapies (Second-line therapy (2L) and higher) with drugs/protocol and dates for start / end	Relevant for outcomes	Medical Chart	y/n; used drugs/regime; start/stop
Concomitant diseases and therapeutic measures	Relevant for outcomes	Medical Chart	Detailed diagnosis; therapeutic measures OP/medicinal/none/other

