9. RESEARCH METHODS

The present 1L treatment of patients with aRCC in Germany is wide-ranging with several options like combinations of ICI + TKI, ICI + ICI or monotherapies with TKI alone. Some of these therapies are only recommended in specific risk situations or in cases of ineligibilities for ICI, but at present there is only limited information available about decisions in 1L aRCC. Additionally, a higher proportion of patients with combined therapies of ICI + TKI or ICI + ICI show intolerabilities with the necessary for dose modifications or interim / permanent discontinuations of one or both drugs, but the processes of decision finding between dose modifications, interruptions and discontinuation are also unclear, although these processes would be very important for the outcomes of the therapy. In contrast to study protocols with clear specifications for handling AEs, in standard daily care the decision processes seem to be in the discretion of every oncologist. But at present, no detailed information about these

processes in standard daily care are available. Such information is also important as these therapies could be administered under in- or out-patient's settings and by urologists or medical oncologists.
Study design

The general design of this data project is a sampling of data about patients with aRCC receiving a 1L therapy, with a start (part 1) or completion (part 2) in 01 January 2020 – 31 December 2021. Data will be documented retrospectively and under full anonymization by investigators or their designees in a specific eCRF. All analyses and reports will be performed under aggregation of data as secondary data reports.

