9.5. Data management

The main purpose of the specific eCRF is to obtain data required by the study protocol in a complete, accurate, legible and timely manner. The data in the eCRF should be consistent with the relevant source documents in the practices and hospitals. The investigator or his/her designee is responsible for ensuring that the data collected in the course of this study are accurate and documented appropriately and completely in all applicable forms. Data will be documented, processed, evaluated, and stored in fully anonymous form in accordance with applicable data protection regulations. The investigator must ensure that the eCRFs and any other associated documents forwarded to the project management contain no mention of any subject names or other personalized information. The data will be entered by the eCRF into a validated database. The project management will be responsible for data processing, in accordance with the Sponsor's data management procedures. The sponsor will receive only full anonymized data or aggregated reports, without any options for re-identification of patients and/or sites. Database lock will occur once quality control and quality assurance procedures and second, that activities of documentation and coding have been completed. The eCRF has a modular structure with separation of contents to build up all sequences and information of treatments from date of first diagnosis up to the present date or death or lost-of-follow-up. Data must be filled in completely and legibly by choosing parameters out of a pre-defined drop-down-list, or in a few cases by writing free text. All corrections will be listed in a history trail with name of corrector and date of correction. Relevant fields are declared as mandatory and must be fulfilled definitively before triggering any payment. As part of the data quality process, all entries in the eCRF will be checked by data manager. In cases of implausibility or incorrectness or inaccuracy or relevant missing data, the data manager together with the medical lead of GermanOncology are allowed to reject patients with a statement of an appropriate reason. Every patient's documentation file is given a randomized code of numbers and letters, automatically generated by an encryption algorithm. As only anonymized data will be sampled, this data handling and storage can be described as "full anonymized" in accordance to the recital 25 of the German and EU General data protection regulation.

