9.7. Quality control

The most relevant step in quality control and quality assurance will be an avoidance of inaccuracies or mismatches in terminology by data entries in data fields over a selection of parameters or descriptions out of pre-defined drop-down-lists. Free text is only intended for descriptions after selection of "other", which will be possible in some data fields, where a pre-definition cannot be

implemented for 100%. For all dates regarding parameters like first diagnosis, pre-treatments, therapy administrations automatic checks are implemented for data entries, so that the course of treatment will be shown correctly (e.g. adjuvant therapy after OP and before palliative therapy, end of 1L before start of 2L, end of therapy after last administration). In defined data fields new explanation fields will open up after selection of specific documentations (e.g. after selection of dose modification query for modified dose, after selection of end of therapy query for reason). In data fields with information like weight, height or age, automatic standard range checks, are implemented to avoid input errors. In addition to these automatic checks every data entry will also be checked by an experienced data manager and, if needed, by the medical lead.

In case of relevant inaccuracy or implausibility, patient's data files will be rejected before further analytical processes will start. After the decision for rejection of patients the investigator will be informed about the reason for rejection and all data will be deleted immediately.

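### Tab. 2 has no code for first-line treatment without an ICI by physician's choice, so guideline adherence of these regimens in Part 1 cannot be classified reliably

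*Combined protocol and SAP*

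**What the plan says.** Tab. 2 in Section 9.2 contains the item "If applicable: Reason for ineligibility of ICI", whose operational definition is "Concomitant disease; patient's wish". No other value is listed.

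Two other reason items in the same table are wider. Reasons for modification or discontinuation are "Each for single/all drugs: intolerance; age; performance status; patient's decision; other". Reasons for the end of first-line therapy are "Progression; intolerance; decision oncologist; patient's wish; death; deterioration performance".

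The item matters because of how the plan summarises the guidelines. Sections 4 and 8 name ICI combinations as the recommended options and list regimens without an ICI for patients who are ineligible for one, by risk group. Section 9 adds: "Some of these therapies are only recommended in specific risk situations or in cases of ineligibilities for ICI". Section 8.1 asks: "How are patients treated in 1L in different risk rating groups and how is the adherence to national/international guidelines". The Abstract calls learning how widely the national guidelines are followed an important objective, and Section 7 makes it part of the rationale.

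On data entry, Sections 9.5 and 9.7 foresee drop-down lists, with free text only where 'other' can be chosen. Section 9.3 says that anonymization makes queries impossible and that patients with relevant missing or implausible data may be rejected. Under Section 9.7 the data of rejected patients are deleted. Section 9.8 requires unavailable data to be marked as such. Section 9.6 leaves the analysis detail to a separate SAP.

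**The concern.** Take a patient with no documented contraindication to an ICI who received a TKI alone because the physician preferred it. Tab. 2 has no value for this case. The site can enter one of the two listed reasons, which makes the patient look ineligible, or leave the item blank. A blank has at least three possible meanings: the patient was eligible, the reason was not on the list, or the item was skipped.

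The adherence question turns on this distinction for every first-line regimen without an ICI. Because queries are excluded, a distinction that was not collected cannot be recovered, and a later SAP can only choose how to count an ambiguous blank. In addition, patient's wish is stored as a reason for ineligibility although it describes a refusal. Nothing says how it is to be counted.

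The effect is confined to Part 1, since Part 2 enrols only ICI combinations. The primary outcome, PFS, is not touched.

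**Working it through.** The documents give no figure for adherence, for the share on TKI monotherapy or for the reasons behind it, so there is no stated figure to reproduce. The check has two steps.

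**1. What the code list can separate (patients treated without an ICI)**

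| True situation | Possible entry under Tab. 2 |
|---|---|
| Ineligible because of a concomitant disease | Concomitant disease |
| Patient declined an ICI | Patient's wish |
| Ineligible for a reason not on the list | Blank, or a listed reason that does not fit |
| Eligible, physician chose otherwise | Blank, or a listed reason that does not fit |
| Chart is silent | Blank, or marked unavailable under Section 9.8 (no code for it in Tab. 2) |

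The last three rows can share the same entry, although they call for different adherence classes.

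**2. What this could do to the adherence figure (illustration only)**

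Inputs:
- Part 1 sample size: 400 (Section 9.4).
- m, the share of Part 1 on TKI monotherapy: assumed 10-40%.
- q, the share of those treated so by physician's choice: assumed 10-50%.
- u, the share of the truly ineligible whose reason is not on the list: assumed 20%, used in (c) only.
- All other patients are taken as adherent, so true adherence is 1 - mq.

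Results:
- (a) Every physician's-choice patient is entered under a listed reason and counted as ineligible. Measured adherence is 1, so the error is +mq. Lowest: 0.10 × 0.10 = 0.01, or 4 of 400 patients, +1 point. Highest: 0.40 × 0.50 = 0.20, or 80 of 400 patients, +20 points.
- (a') These patients are rejected instead. Measured adherence is (1 - mq)/(1 - mq) = 1, so the error is again +mq.
- (b) They are left blank, and blank counts as non-adherent. Measured adherence is 1 - mq, so the error is 0.
- (c) As (b), but truly ineligible patients with an unlisted reason are also blank. Measured adherence is 1 - mq - m(1 - q)u, so the error is -m(1 - q)u. Smallest: 0.10 × 0.50 × 0.20 = 0.01, or -1.0 point. Largest: 0.40 × 0.90 × 0.20 = 0.072, or -7.2 points.

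A mid-range example, m = 20% and q = 25%: (a) gives 0.20 × 0.25 = +5 points (20 patients), (b) gives 0, and (c) gives 0.20 × 0.75 × 0.20 = -3 points.

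Counting patient's wish as ineligibility would add to any overstatement. It is not in these figures because the list does record it as its own value.

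**A related inconsistency.** For ICI-ineligible intermediate-risk patients, Section 4 lists cabozantinib, pazopanib, sunitinib and tivozanib, while Section 8 lists cabozantinib and sunitinib. A patient on pazopanib or tivozanib would be classed differently depending on which section is used.

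**The case against.** A reader might infer that adherence is overstated and that the error can only run in that direction. The documents do not support this. The item is headed as applying only where relevant, so an ICI-eligible patient may properly have no entry. The regimen is recorded separately, so a TKI without any ineligibility reason remains visible as a possible non-adherent case. No adherence rule is given, and depending on that rule the error is positive, zero or negative.

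A reader might also infer that sites are paid to pick a listed reason. Section 9.5 says "Relevant fields are declared as mandatory and must be fulfilled definitively before triggering any payment", but does not say that this conditional item is one of those fields. The pressure is possible, not shown.

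Other points on this side are fair:
- Section 9.8 requires unavailable data to be marked, which narrows what a blank can mean. It still does not separate an eligible patient from an unlisted reason or a skipped item.
- Concomitant diseases are captured in detail, so that reason can be checked for plausibility. A recorded disease does not show that it was why the ICI was withheld.
- Patient's wish is its own value and can be reported separately. What is missing is the rule for counting it.
- Adherence is not among the objectives in Section 8.2 or the listed outcomes. The listed comparison by specialty and institution concerns the distribution of therapies and modifications. The therapy distribution rests on the recorded regimen, so no damage to it follows from this item.
- The 5% margin in Section 9.4 was set for PFS rates and is not a yardstick for an adherence error.
- Adherence depends on risk group as well as on eligibility.
- The final eCRF and the separate SAP are not in the documents, so further codes there cannot be excluded. If they exist, Tab. 2 should show them.

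These points remove the claim of a fixed direction and limit the scope. They do not supply the missing codes.

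**Conclusion.** The concern holds as a gap in classification. As Tab. 2 stands, the adherence of Part 1 first-line regimens without an ICI cannot be classified reliably, and neither queries nor a later SAP can repair this. Adherence is overstated if physician's choice is entered under a listed reason, if patient's wish is counted as ineligibility, or if incomplete patients are rejected. It is unbiased or understated if blanks count as non-adherent.

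The size is unknown. The range of about +20 to about -7 percentage points rests wholly on the assumed shares and shows only that the coding rule could matter. It is not an estimate. The point weakens the answer to a stated research question and leaves the primary outcome and Part 2 unaffected.

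**What to change.** Before data collection (planned from 1 October 2022), replace the item in Tab. 2 and in the Abstract by two items, required for every first-line regimen without an ICI:

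- (a) ICI ineligibility documented in the chart: yes / no / not documented.
- (b) Reason for not using an ICI: concomitant disease / patient's wish / physician's decision / other (free text) / not documented.

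In the protocol or SAP, state how each combination of codes maps to adherent, non-adherent or not classifiable within each risk group. Report patient's wish and not documented as separate rows. Give best-case and worst-case bounds, counting all unclassifiable patients first as adherent and then as non-adherent. Reconcile the drug lists for ICI-ineligible intermediate-risk patients in Sections 4 and 8 before adherence is coded.

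The cost is one extra item, a few drop-down values and a short mapping table. The downside is a visible not-documented share in the report.
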